| | A positive result for HBV DNA PCR testing in these subjects will require immediate interruption of study drug (per local guidelines) and a hepatologist consultation should occur within 1 week for recommendation regarding subsequent treatment. |
| Serum Creatinine | • If serum creatinine is > 1.5 × the baseline value and > ULN, repeat the test for serum creatinine (with subject in an euvolemic state) to confirm the results. If the results of the repeat testing still meet this criterion then interrupt study drug and re-start study drug once serum creatinine returns to ≤ 1.5 × baseline value and ≤ ULN. |
| | If confirmed new serum creatinine ≥ 2 mg/dL, interrupt study drug and re-start study drug once serum creatinine returns to normal reference range or its baseline value. |
| | For the above serum creatinine elevation scenarios, complete supplemental renal eCRF(s). |

| Laboratory Parameters | Toxicity Management Guidelines |
|-----------------------------------|--|
| Creatine Phosphokinase (CPK) | CPK and aldolase will be measured at every visit, but results will be blinded to sites and subjects, as CPK elevation is a known class effect of JAK inhibitors and the results could be unblinding to the sites. If symptomatic myositis is suspected, the site may send a request to the AbbVie TA MD for CPK and/or aldolase results to be unblinded. Request must be approved by the AbbVie TA MD. |
| | If confirmed CPK ≥ 4 × ULN accompanied by symptoms suggestive of myositis or rhabdomyolysis, interrupt study drug, complete supplemental CPK eCRF, and contact the AbbVie TA MD. |
| Lymphocyte Count Decreased | • If confirmed Grade 4 (< 200/mm³) by repeat testing with new sample, interrupt study drug dosing until lymphocyte count returns to at least Grade 2 (< 800 to 500/mm³) or its baseline value. |
| White Blood Count Decreased | If confirmed Grade 4 (<1000/mm³) by repeat testing with new sample, interrupt study drug dosing until white blood cell count returns to at least Grade 2 (< 3000 to 2000/mm³) or its baseline value. |
| Urine Protein to Creatinine Ratio | If > 2 g/day equivalent (2 mg/mg), repeat by testing with new sample, and if confirmed, a renal biopsy will be required. |
| | If Class IV lupus nephritis is confirmed, subject must be permanently discontinued from study drug. |

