9.0 Safety Analyses

9.1 General Considerations

Safety analyses will include reporting of adverse events, laboratory, and vital signs measurements based on data in Study M20-186. Safety analyses will be carried out using the Safety Analysis Set.

The following summary statistics will be presented for subjects who have both baseline and post-baseline values for laboratory parameters and vital signs: the mean value at Baseline and at each respective protocol specified visit, and the mean, standard deviation and median for changes from Baseline. Categorical data will be summarized using frequencies and percentages. The number of non-missing values will be given. Missing safety data will not be imputed.

For safety analysis, Baseline is defined as the last available measurement before Study M19-130 study drug administration if the subjects took active treatment in Study M19-130, and the last available measurement before Study M20-186 study drug administration if the subjects took placebo in Study M19-130.

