9.3 Analysis of Laboratory Data

Data collected from central and local laboratories, including additional laboratory testing due to an SAE, will be used in all analyses, except for Baseline, where SAE-related laboratory assessments on or before the first dose of study drug will be excluded. The clinical laboratory tests defined in the protocol operations manual (e.g., hematology and clinical chemistry) will be summarized.

Each laboratory variable will be summarized for all time points (starting with Baseline) with the number of non-missing observations, mean and standard deviation, median, minimum and maximum.

Mean change from Baseline to each applicable post-Baseline visit will be summarized for selected laboratory variables, with the number of observations, Baseline mean, and visit mean, at each visit in Study M20-186 for each treatment group. The change from Baseline mean, standard error, and 95% confidence interval will be presented for the mean change from Baseline within each treatment group.

Shift tables will be provided for each hematology, clinical chemistry parameter. Shifts from Baseline to the following endpoints will be considered: post-Baseline value and final value. This analysis will be performed only for category of "low or normal" at Baseline which shift to 'high' and category of "high or normal" at Baseline which shift to category of 'low.'

For selected laboratory variables including hemoglobin, neutrophils, lymphocytes, platelets, creatinine, ALT, AST, CPK, LDL cholesterol, HDL cholesterol, total cholesterol, and triglycerides, a listing of all observations collected will be generated for subjects that had at least one post-Baseline observation meeting pre-defined criteria for potentially clinically important values. The number and percentage of subjects in each treatment group who have at least one post-Baseline observation meeting the pre-defined criteria for potentially clinically important values will be provided for each variable. The criteria for potentially clinically important laboratory values will be determined by NCI CTCAE version 4.03 of greater than Grade 3 or greater than Grade 4.

For the purpose of assessing for potential Hy's law cases, the frequencies and percentages of subjects with post baseline liver-specific function test values that meet the following criteria of potential clinical interest will be summarized by "as treated" treatment group:

- $ALT \geq 3 \times ULN$
- $ALT \geq 5 \times ULN$

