Appendix C. Potentially Clinically Important Criteria for Vital Sign Values

Vital Sign	Category	Criteria for Potential Clinically Important Vital Signs
Systolic blood pressure	Low	Value \leq 90 mmHg and decrease \geq 20 mmHg from Baseline
	High	Value \geq 160 mmHg and increase \geq 20 mmHg from Baseline
Diastolic blood pressure	Low	Value \leq 50 mmHg and decrease \geq 10 mmHg from Baseline
	High	Value \geq 100 mmHg and increase \geq 10 mmHg from Baseline
Weight	High	> 7% increase from baseline
	Low	> 7% decrease from baseline

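### Laboratory PCI counts in SAP 9.3 do not require a grade worse than Baseline, so severe values that predate active drug are tabulated together with those that arose later

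*SAP*

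**What the plan says.** **Counting rule.** SAP 9.3 tabulates, per treatment group, the subjects "who have at least one post-Baseline observation meeting the pre-defined criteria for potentially clinically important values will be provided for each variable". The scope is given by "For selected laboratory variables including hemoglobin, neutrophils, lymphocytes, platelets, creatinine, ALT, AST, CPK" and the lipid fractions.

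**Criterion.** The thresholds "will be determined by NCI CTCAE version 4.03 of greater than Grade 3 or greater than Grade 4". There is no further term about the Baseline value or grade. Protocol 7.4, which announces the same summary, has none either.

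**Baseline.** SAP 9.1 defines a safety Baseline that precedes active drug in every group. For one set of subjects it is "the last available measurement before Study M19-130 study drug administration if the subjects took active treatment in Study M19-130". Those who come from the feeder study's control arm have a later reference point, namely "the last available measurement before Study M20-186 study drug administration if the subjects took placebo in Study M19-130". SAP 9.1 also fixes the data scope: "Safety analyses will include reporting of adverse events, laboratory, and vital signs measurements based on data in Study M20-186".

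**Vital signs, under the same PCI label.** SAP Appendix C has six criteria: low and high for systolic pressure, diastolic pressure and weight. The four blood-pressure criteria pair an absolute limit with a minimum change from Baseline. The two weight criteria are a change alone, for example "> 7% increase from baseline".

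**Other laboratory outputs in SAP 9.3.** These are means and mean changes from Baseline, shift tables across low, normal and high, and a listing of every observation for each subject who meets a PCI criterion.

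**The concern.** The laboratory PCI table is the planned summary of severe laboratory values, and safety is the primary objective. A subject whose severe value predates active drug and persists or recurs in the extension enters that table in the same way as a subject who moved into the severe range after Baseline. The percentage mixes the two, and the table gives no means of separating them.

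Three features of the trial make this worth attention. There is no placebo arm (Protocol 4.2), so no concurrent untreated group shows how much of a PCI percentage is background. Anemia, neutropenia and lymphopenia are named as potential upadacitinib risks (Protocol 2.2) and as events of special interest (Protocol 6.1), and the corresponding laboratory variables are in this table. The groups are small, so one or two subjects visibly move a percentage.

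**Working it through.** **1. Is there a worsening condition anywhere?**

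| Output | Condition on Baseline |
|---|---|
| Laboratory PCI count (SAP 9.3) | None |
| Same summary in Protocol 7.4 | None |
| Vital-sign PCI (SAP Appendix C) | Change from Baseline in all six criteria |
| Laboratory shift tables (SAP 9.3) | Subjects already in the target category are left out, but categories are low/normal/high, not grades |
| Laboratory listing (SAP 9.3) | All observations shown; the tabulated count is unchanged |

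A subject below normal at Baseline is outside the shift-to-low table. If such a subject goes from mildly low to severe, or was severe throughout, neither shift table shows it and the PCI table shows both cases alike. Group means cannot tell them apart either.

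**2. Do the documents allow for a severe Baseline value?** Protocol Table 4 says, for lymphocytes, "interrupt study drug dosing until lymphocyte count returns to at least Grade 2", a band it gives as 500 to below 800/mm³, or else to the subject's own Baseline value. That second route adds something only if Baseline lies below 500/mm³. The documents therefore contemplate such Baselines. They give no frequency.

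**3. Does the cut-off matter?** Table 4 puts Grade 4 lymphocytes below 200/mm³ and the floor of Grade 2 at 500/mm³, so 200 to below 500/mm³ is Grade 3. Take a subject at 400/mm³ at Baseline and 450/mm³ in the extension. If the cut-off means Grade 3 or worse, this subject is counted although the value rose. Read literally, above Grade 3 starts below 200/mm³ and the subject is not counted. A subject at 150/mm³ both times would be counted under either of these two readings. The rule lacks a Baseline condition wherever the cut-off is set; only the number affected changes.

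**4. Group sizes.** Protocol 4.1 projects 65 subjects in each of 5 groups.

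- Reproducing the plan's figure: 5 × 65 = 325; 0.60 × 325 = 195; 0.80 × 325 = 260. This matches the stated 195 to 260.
- Continuing group: 65 × 0.60 = 39 to 65 × 0.80 = 52, assuming the same rollover share in each group.
- Groups 5a and 5b, using the 1:1 split described for the period before the M19-130 interim analysis: 39 / 2 = 19.5 to 52 / 2 = 26.

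**5. Effect of one carried-in subject.**

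- Continuing group: 100 / 52 = 1.9 to 100 / 39 = 2.6 percentage points.
- Group 5a or 5b: 100 / 26 = 3.8 to 100 / 19.5 = 5.1 percentage points.

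**6. Illustration over a range of assumptions.** Let b be the share with a qualifying grade at Baseline, s the share of those with a qualifying value again in the extension, and q the rate of newly qualifying values among the rest. None of these is in the documents. Suppose also that the carried-in subjects do not go to a still higher grade.

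- Counted under SAP 9.3: b × s + (1 − b) × q
- Worse than Baseline: (1 − b) × q

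With q = 2% and s from 50% to 100%:

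| b | Counted now | Worse than Baseline |
|---|---|---|
| 0% | 2.0% | 2.0% |
| 1% | 2.5% to 3.0% | 2.0% |
| 5% | 4.4% to 6.9% | 1.9% |
| 10% | 6.8% to 11.8% | 1.8% |

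The chance that a group of 39 to 52 holds at least one subject with a qualifying Baseline grade is 1 − (1 − b)^n. That is 0% at b = 0%, 32% to 41% at b = 1%, 87% to 93% at b = 5%, and 98% to over 99% at b = 10%.

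**The case against.** Counting absolute thresholds is a recognised convention, and this SAP uses it elsewhere. The liver thresholds in SAP 9.3 and the QTcF limit of 500 msec in SAP 9.6 are also counted without reference to Baseline, and the laboratory rule agrees with Protocol 7.4. A reader might infer that the laboratory PCI table is the only one without a Baseline condition; that is not so. What stands is the narrower contrast with Appendix C, where the same PCI label carries a change requirement.

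Change from Baseline is also covered by mean changes, shift tables, the listing, and adverse-event reporting of anemia, neutropenia and lymphopenia. This is fair, and a careful reader of the listing could find the Baseline values. None of these outputs, however, splits the PCI percentage into worsened and not worsened.

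Three stronger readings are tempting and should not be made.

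- That every subject entering with a cytopenia is counted. A qualifying value must also occur in the extension, so only persistent or recurrent abnormality matters.
- That the rates are inflated by some definite amount. The M19-130 laboratory entry limits and Baseline grades are not in these documents. If those limits exclude such grades, the number could be near zero, particularly under the literal cut-off.
- That each percentage will be taken directly as a drug effect. Protocol 4.2 names each group's safety profile in the randomized study as the primary comparison. All summaries are descriptive, so no test or type I error is affected.

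Finally, replacing the count by one restricted to worsening would have its own cost. For active-treated subjects Baseline precedes M19-130 dosing. Someone at Grade 3 then, Grade 1 at Week 48, and Grade 3 again in the extension would drop out, although this is deterioration on study. That objection is sound and shapes the fix.

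**Conclusion.** The point holds as a gap in presentation. The laboratory PCI count cannot distinguish a severe value carried in from before active drug from one that is worse than Baseline, and no other planned table makes the distinction by grade. The gap covers every variable in the table, not only blood counts, and bears on the primary safety objective.

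Its total size is unknown. The per-subject effects in the working rest on the projected 65 per group, equal rollover of 60% to 80%, and the pre-interim 1:1 split; the SAP warns that the groups may change after the M19-130 interim analysis. Prevalence and persistence are assumptions whose range starts at zero. The wording of the grade cut-off is a separate matter that needs clarifying in its own right. This is a cheap and worthwhile improvement, not evidence that the reported rates will be wrong by a known margin.

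**What to change.** In SAP 9.3, keep the existing all-values count and do one of the following:

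- report next to it the count and percentage of subjects whose qualifying post-Baseline grade is worse than their Baseline grade, with Baseline as in SAP 9.1; or
- add a table of Baseline grade by worst post-Baseline grade for each selected variable and treatment group.

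In either case, show the Baseline grade in the PCI listing. State in a footnote that worse than Baseline means worse than before active drug, not necessarily first seen in the extension.

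The cost is one SAP sentence, one programming condition, and one extra column or table, all from data already collected. The worsening count alone would miss worsening within a grade and return to the Baseline grade after improvement. The all-values count should therefore stay beside it.

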Such an event can result from use of the drug as stipulated in the protocol, as well as from accidental or intentional overdose, drug abuse, or drug withdrawal. Any worsening of a pre-existing condition or illness is considered an AE. Worsening in severity of a reported AE should be reported as a new AE. Laboratory abnormalities and changes in vital signs are considered to be AEs only if they result in discontinuation from the study, necessitate therapeutic medical intervention, meet protocol-specific criteria (see Section 6.2 regarding toxicity management), and/or if the investigator considers them to be AEs. Worsening SLE including flares will be captured and analyzed via the disease activity forms (SLEDAI, BILAG, CLASI, and SFI) and will be analyzed as part of efficacy. As such, worsening SLE and flares will not be captured as AEs unless they result in serious outcomes.

The investigators will monitor each subject for clinical and laboratory evidence of AE on a routine basis throughout the study. All AEs will be followed to a satisfactory conclusion.

An elective surgery/procedure scheduled to occur during a study will not be considered an AE if the surgery/procedure is being performed for a pre-existing condition and the surgery/procedure has been pre-planned prior to study entry. However, if the pre-existing condition deteriorates unexpectedly during the study (e.g., surgery performed earlier than planned), then the deterioration of the condition for which the elective surgery/procedure is being done will be considered an AE. If the subject undergoes elective surgery, the study drug should be interrupted at least 1 week prior to the planned surgery. If the subject must undergo emergency surgery, the study drug should be interrupted at the time of the surgery. For both elective and emergency surgery, allow reintroduction of study drug once the physician has examined the surgical site and determined that it has healed and there is no sign of infection.

If any of the following events (Table 3) are reported, then the following supplemental report must be completed.

Table 3. Adverse Events Requiring Supplemental Reports

| Adverse Events | Supplemental Report |
|----------------------|---|

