The following adverse events of special interest (AESI) will be routinely monitored during the study:

- Serious infections
- Opportunistic infections
- Herpes zoster
- Active TB
- Malignancy (all types)
- Adjudicated GI perforations
- Adjudicated cardiovascular events (e.g., MACE)
- Anemia
- Neutropenia
- Lymphopenia
- Renal dysfunction
- Hepatic disorders
- Adjudicated embolic and thrombotic events (non-cardiac, non-CNS) including venous thromboembolic events defined as pulmonary embolism and deep vein thrombosis.

Adverse Event Severity and Relationship to Study Drug

Investigators will rate the severity of each AE according to the National Cancer Institute (NCI) Common Terminology Criteria for Adverse Events (CTCAE) version 5, which can be accessed at: https://ctep.cancer.gov/protocoldevelopment/electronic_applications/docs/ctcae_v5_quick_reference_8.5x11.pdf.

If no specific grading criteria are provided for the reported event, then the event should be as follows:

- Mild (Grade 1): asymptomatic or mild symptoms; clinical or diagnostic observations only; intervention not indicated;
- Moderate (Grade 2): minimal, local or noninvasive intervention indicated; limiting
 age-appropriate instrumental activities of daily living (ADL) (instrumental ADL refer to preparing
 meals, shopping for groceries or clothes, using the telephone, managing money, etc.);
- Severe (Grade 3 5):
 - Grade 3: severe or medically significant but not immediately life-threatening; hospitalization or prolongation of hospitalization indicated; disabling; limiting self-care ADL (self-care ADL refers to bathing, dressing and undressing, feeding self, using the toilet, taking medications, and not bedridden);

- Grade 4: Life-threatening consequences; urgent intervention indicated;
- Grade 5: Death related to AE.

The investigator will use the following definitions to assess the relationship of the AE to the use of study drug:

| Reasonable Possibility | After consideration of factors including timing of the event, biologic plausibility, clinical judgment, and potential alternative causes, there is sufficient evidence (information) to suggest a causal relationship. |
|------------------------------|--|
| No Reasonable Possibility | After consideration of factors including timing of the event, biologic plausibility, clinical judgment, and potential alternative causes, there is insufficient evidence (information) to suggest a causal relationship. |

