9.2.3 Treatment-Emergent Adverse Events by SOC and/or PT

Treatment-emergent adverse events will be summarized by SOC and PT; by maximum relationship to study drug as assessed by the investigator (e.g., reasonable possibility or no reasonable possibility) and SOC and PT; by maximum toxicity grade and SOC and PT; and by subject number and SOC and PT. Specific adverse events will be counted once for each subject for calculating percentages, unless stated otherwise. In addition, if the same adverse event occurs multiple times within a subject, the maximum toxicity grade and level of relationship to investigational product will be reported.

In addition, treatment-emergent adverse events will be summarized by PT and sorted by decreasing frequency for the total active group.

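### As worded, the laboratory PCI cut-off in SAP 9.3 leaves out subjects whose worst value is Grade 3, and its second tier is empty

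*SAP*

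**What the plan says.** SAP 9.3 plans two PCI outputs for twelve laboratory variables: hemoglobin, neutrophils, lymphocytes, platelets, creatinine, ALT, AST, CPK and four lipids. One is a table of the number and percentage of subjects per treatment group with at least one qualifying post-Baseline value. The other is a listing of every observation for those subjects. Both use the same rule: the criteria are "determined by NCI CTCAE version 4.03 of greater than Grade 3 or greater than Grade 4".

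No other text defines the laboratory criteria. Protocol 7.4 promises the percentage of subjects meeting pre-defined PCI criteria but names no grade. SAP Appendix C gives PCI limits for vital signs only.

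On the grades themselves, Protocol 6.1 ends its general severity scale with "Grade 5: Death related to AE". Table 4 in Protocol 6.2 gives two lymphocyte bands. The action rule begins "If confirmed Grade 4 (< 200/mm³) by repeat testing with new sample", and dosing stays interrupted until the count "returns to at least Grade 2 (< 800 to 500/mm³) or its baseline value".

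**The concern.** A programmer who follows the sentence would code a strict inequality. It would run without error and return low but plausible counts, so the mistake could go unnoticed. The SAP does distinguish the two forms elsewhere. It uses greater-than-or-equal signs for the liver thresholds that follow in the same section and for blood pressure in Appendix C, and a strict sign for the transaminase part of the Hy's law listing. Nothing therefore tells the reader to take this sentence as inclusive.

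Safety and tolerability are the study's primary objective. The PCI table is the only planned count of subjects by laboratory grade. If Grade 3 is left out of it, a subject with a marked laboratory change may be counted in no graded summary at all.

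**Working it through.** The plan gives no figure to reproduce here. The check applies the rule as written and then asks whether another output fills the gap.

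**Step 1. Apply the cut-offs.** Take laboratory grades as 0 to 4, with Grade 5 meaning death (Protocol 6.1).

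| Cut-off | Laboratory grades selected |
|---|---|
| > 3 (as written) | 4 |
| > 4 (as written) | none |
| > 3 or > 4 (as written, joined) | 4 |
| ≥ 3 | 3 and 4 |
| ≥ 4 | 4 |

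The open-ended Grade 4 lymphocyte band in Table 4 (below 200/mm³, with no lower limit) agrees with an empty tier above Grade 4.

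**Step 2. Who is lost.** The listing prints all observations of any subject who qualifies. A Grade 3 value is therefore still listed if the same subject also reaches Grade 4 on that variable. The subjects missing from both outputs are those whose worst post-Baseline value is Grade 3.

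**Step 3. An example from the protocol's own bands.** Grade 2 is 500 to below 800/mm³ and Grade 4 is below 200/mm³, so Grade 3 is 200 to below 500/mm³. A subject who falls from 600 at Baseline (Grade 2) to 300 (Grade 3) is not flagged as PCI. The Grade 3 band is inferred from Table 4, which names no CTCAE version. The version 4.03 tables are not in the documents.

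**Step 4. Do other outputs replace the count?**

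- *Shift tables (SAP 9.3).* "This analysis will be performed only for category of" low or normal moving to high, and high or normal moving to low. If 600 is already below the laboratory's lower limit, the subject in Step 3 is not counted. The tables also carry no grade.
- *AE tables (SAP 9.2.3).* These are produced "by maximum toxicity grade and SOC and PT", but a laboratory value must first be an AE. Protocol 6.1 says: "Laboratory abnormalities and changes in vital signs are considered to be AEs only if they result in discontinuation from the study". The same sentence adds three further routes: needing therapeutic medical intervention, meeting a protocol-specific criterion, or the investigator's own judgment. For lymphocytes, Table 4 acts only at Grade 4, so a Grade 3 count need not become an AE.
- *AESI summaries (SAP 9.2.6 and Appendix B).* Anemia, neutropenia and lymphopenia are found by queries on reported AEs, so they share that limit. CPK is not on the list.
- *CPK.* Table 4 says: "CPK and aldolase will be measured at every visit, but results will be blinded to sites and subjects". The site does not see a symptom-free rise and so cannot report it as an AE.
- *By-visit minimum and maximum.* These give one extreme value per group and visit, not a number of subjects.
- *ALT and AST.* These are covered separately, by counts at 3, 5, 10 and 20 × ULN.

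**Step 5. Effect of each omitted subject.** Protocol 4.1 projects 65 per arm in Study M19-130. SAP 2.4 expects 60% to 80% to roll over.

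- Continuing group: 0.60 × 65 = 39 and 0.80 × 65 = 52. One subject is 1/52 = 1.9% to 1/39 = 2.6%.
- Former-placebo groups 5a and 5b, split 1:1: 39/2 = 19.5 and 52/2 = 26 on average. One subject is 1/26 = 3.8% to 1/19.5 = 5.1%.

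**The case against.** The strongest reply is that this is a drafting slip which a competent programmer would query, because a two-tier rule with an empty second tier makes no sense. That is likely, and the documents cannot show what would be coded. But the sentence is the only operative definition, so the plan should not depend on someone noticing.

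The second reply is that much of the information arrives by other routes. Table 4 sets criteria for hemoglobin, neutrophils, platelets and creatinine, and values meeting them become AEs and reach the tables by maximum grade. Anemia, neutropenia, lymphopenia and renal dysfunction are also AESIs. A CPK rise from normal to high shows in the shift tables. This is fair and narrows the consequence: the clearest gaps are Grade 3 lymphocyte counts and symptom-free CPK rises. The other routes are still partial, and none is a graded count of laboratory values.

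Third, the per-subject effect is simply one over the group size, and the group sizes may be wrong. The summary of changes in the protocol says that treatment groups were selected after the feeder study's interim analysis. The 1:1 placebo split is described as applying before it. This stands: the percentages are illustrative, not an estimate of how much is lost.

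Fourth, the meaning of Grade 5 comes from the protocol's general AE scale under CTCAE version 5, whereas the SAP grades laboratory values by version 4.03. The empty second tier is therefore an inference from the documents, though the open-ended Grade 4 band supports it.

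Finally, no hypothesis is tested, a data monitoring committee sees unblinded safety data, and the SAP's version history defers integrated summaries to a later submission. These limit the consequence but do not correct the sentence.

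**Conclusion.** The concern holds and should be fixed. Read as written, the laboratory PCI rule flags Grade 4 only, its second tier selects nothing, and no other text restores Grade 3. Subjects whose worst post-Baseline value is Grade 3 are lost from both the PCI table and the PCI listing, most clearly for lymphocytes and CPK.

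Confidence is high on the wording and on what it selects. The total effect cannot be stated, because the documents do not say how many subjects have Grade 3 as their worst value. The per-subject effect in Step 5 rests on equal rollover across the five arms, no arm dropped, a 1:1 placebo split, and all enrolled subjects in a group counted in the denominator. That the sponsor meant inclusive cut-offs is also an assumption, though the likeliest one.

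**What to change.** Reword the sentence in SAP 9.3 so that the laboratory PCI criteria are *CTCAE Grade 3 or higher (≥ 3) and, separately, Grade 4 or higher (≥ 4)*, and state that the same cut-offs apply to the PCI table and the PCI listing. If the sponsor really intends Grade 4 only, the SAP should say so and drop the empty tier. Either way the sentence has to change.

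The cost is one SAP sentence and the matching inequality in the program. The table and listing may include more subjects. No new data are needed, and no clinical management rule is affected.
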